PtGADA Patient's Global Assessment of Disease Activity

QoL quality of life

RA rheumatoid arthritis
SAE serious adverse event
SJC swollen joint count

SmPC summary of product characteristics

SOC system organ class

SOP standard operating procedure

SS	Safety Set
TEAE	treatment emergent adverse event
TJC	tender joint count
$TNF\alpha$	tumor necrosis factor alpha
VAS	visual analogue scale

Confidential Page 11 of 89

1 SUMMARY

This is an observational, noninterventional, noncomparative, postauthorization safety study designed to assess the safety and efficacy of certolizumab pegol (CZP) in long-term use (2 years) in standard daily clinical practice. The observational nature of the study leaves the therapeutic decision exclusively within the discretion of the physician. Procedures and assessments are not to go beyond what is standard in clinical practice. Treatment is only to follow standard medical practice as decided by the physician and as directed in the current Summary of Product Characteristics (SmPC).

The primary objective is to assess the clinical efficacy of CZP in achieving clinical remission after 2 years of therapy in adult patients with rheumatoid arthritis (RA). The secondary objective is to assess the effect of treatment with CZP on patients' arthritis pain, physical function, and the Clinical Disease Activity Index (CDAI) after 2 years of therapy. Other objectives include the assessment of clinical remission, identification of responders to treatment, pharmacoeconomics, change in arthritis pain, fatigue, and physical function per visit, and information on the prescribing habits of physicians with regards to the concomitant treatment.

The primary efficacy variable is clinical remission at Visit 9 (around Week 104) (defined as 28-joint count Disease Activity Score [DAS28 of <2.6]). Other efficacy variables include change from Baseline in patient's arthritis pain, levels of fatigue, health status, and physical functions assessed by the patient, clinical remission by visit, and pharmacoeconomic information.

Management of adverse events (AEs) will be handled according to drug safety regulations in Germany.

A total of 1068 patients across 160 sites in Germany are planned to be observed in this study. It is anticipated that the study will run from Q3 2009 (First Patient First Visit) to Q4 2014 (Last Patient Last Visit). The maximum duration of participation for individual patients will be 116 weeks.

2 INTRODUCTION

This noninterventional, postauthorization safety study is designed to assess the efficacy and safety of CZP in long-term use (2 years) in standard clinical practice according to the instructions for the use in patients with RA as described in the SmPC.

Rheumatoid arthritis is a chronic systemic inflammatory disease that is associated with significant morbidity and mortality. The disease is characterized by inflammation of the synovial lined diarthrodial joints that can result in pain, swelling and joint damage with secondary deformity and progressive disability and impairment of patient health related quality of life (QoL). It is estimated that about 1% of the population worldwide has RA.

Certolizumab pegol is a recombinant, humanized antibody Fab'-fragment that is produced in an *Escherichia coli* expression system. The antibody fragment is subsequently purified and conjugated with high molecular weight polyethylene glycol (40kDA).

Certolizumab pegol has a high affinity for human tumor necrosis factor alpha (TNF α) and binds with a dissociation constant of 90pM. Tumor necrosis factor alpha is a key proinflammatory cytokine with a central role in inflammatory processes. Certolizumab pegol selectively neutralizes TNF α (Inhibitory Concentration at 90% of 4ng/mL for inhibition of human TNF α in the in vitro L929 murine fibrosarcoma cytotoxicity assay) but does not neutralize lymphotoxin α (TNF beta).

Certolizumab pegol was shown to neutralize membrane-associated and soluble human TNF α in a dose-dependent manner. Incubation of monocytes with CZP resulted in a dose-dependent inhibition of lipopolysaccharide-induced TNF α and IL1 β production in human monocytes. Certolizumab pegol does not contain a fragment crystallizable region, which is normally present in a complete antibody, and therefore does not fix, complement, or cause antibody-dependent, cell-mediated cytotoxicity in vitro. It does not induce apoptosis in vitro in human peripheral blood-derived monocytes or lymphocytes, or neutrophil degranulation.

Certolizumab pegol is approved in the European Union, Switzerland, the United States, and Canada for the treatment of adults with moderately to severely active RA. Certolizumab pegol can be given as monotherapy or concomitantly with methotrexate or nonbiological DMARDs.

In placebo-controlled trials in adult patients with active RA (see SmPC), CZP has been shown to improve signs and symptoms, physical function, fatigue, health-related QoL, and RA-related productivity (at work and within the home), and inhibit the progression of structural damage.

The formation of antibodies to CZP is associated with lowered drug plasma concentrations and in some patients reduced efficacy. Approximately 7.7% of patients in Phase 3 trials (see SmPC) had antibodies to CZP, of which one third had antibodies with neutralizing activity in vitro. Patients treated with concomitant immunosuppressants had a lower rate of antibody development than patients who had not been taking immunosuppressants at Baseline.

The current study aims to assess efficacy and safety data collected in a real life setting in a defined patient population (age, gender, etc.). Identified and potential risks of CZP treatment can be taken from the current version of the SmPC.

Since the study patients will receive CZP in accordance with the SmPC guidance, the risk for the patients is not considered to be increased as a result of their participation in this noninterventional study.

3 STUDY OBJECTIVES

3.1 Primary objective

The purpose of this study is to assess the clinical efficacy of CZP in achieving clinical remission (DAS28 of <2.6) after 2 years of therapy in adult patients with RA.

3.2 Secondary objectives

The secondary objective is to assess the effect of treatment with CZP on patients' arthritis pain, physical function, and disease activity after 2 years of therapy.

3.3 Other objectives

- Assessment of clinical remission and low disease activity for all patients by visit and for different patient populations, based on DAS28 and American College of Rheumatology (ACR)/European League Against Rheumatism (EULAR) 2011 remission criteria
- Identification of responder/nonresponder to CZP treatment as basis for subgroup classification. A patient is considered to be a responder if the DAS28 decrease is ≥1.2 (see Section 12.3.1)
- Gather information on prescribing habits of the rheumatologists with regards to the concomitant treatment
- Gather information on prescribing habits of rheumatologists with regards to the concomitant RA treatment as well as subsequent treatments in case of CZP discontinuation
- Assess incidence of CZP discontinuation due to remission (DAS28)
- To evaluate and assess the effect of treatment over time with CZP for the following:
 - Arthritis pain (Arthritis pain visual analogue scale [VAS])
 - Fatigue (Fatigue Assessment Scale)
 - Physical function (HAQ-DI) and health related quality of life (EQ-5D)
 - Selected components of the American College of Rheumatology diagnostic and improvement criteria: morning stiffness, tender joint count (TJC), swollen joint count (SJC), C-reactive protein (CRP), or erythrocyte sedimentation rate (ESR)
 - Disease activity (CDAI)
 - Pharmacoeconomic data (missing days at work and employment information)
 - Duration of morning stiffness (in hours)

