4.1.3 Other efficacy variables

- Clinical remission (DAS28 of <2.6) by visit
- Low disease activity (DAS28 of \leq 3.2) by visit
- Proportion of patients achieving clinical response to treatment based on DAS28 reduction of ≥1.2 by visit
- Change from Baseline CDAI by visit
- Change in patient's arthritis pain as measured by Patient's Assessment of Arthritis Pain VAS by visit
- Change from Baseline in patient's fatigue as measured by Fatigue Assessment Scale by visit
- Change from Baseline in patient's physical function as measured by the HAQ-DI (Fries et al, 1980 and Lautenschläger et al, 1997) by visit
- Change from Baseline in health-related QoL measured as EQ-5D by visit, using the VAS part of the EQ-5D.
- Change from Baseline in quantity of concomitant DMARDs
- Change from Baseline in quantity of concomitant corticosteroids
- Incidence of discontinuation of CZP treatment due to DAS28 (CRP) remission
- Change from Baseline in duration of morning stiffness (in hours) by visit
- Change from Baseline in number of swollen and tender joints by visit (joint scores –TJC and SJC)
- Proportion of patients in clinical remission as defined by the ACR/EULAR 2011 remission criteria
- Employment status

- Employability due to RA
- Sick leave
- RA treatment following discontinuation of CZP

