6 SELECTION AND WITHDRAWAL OF PATIENTS

6.1 Inclusion criteria

Patients must fulfill the following inclusion/exclusion criteria at the start of CZP treatment:

- 1. Before any data are collected on study-specific forms for a patient in this noninterventional PASS, written data consent will be properly executed and documented. The patient is informed and given ample time and opportunity to think about his/her participation and has given his/her written consent on the use of data. Note: A patient may be enrolled into the study after the start of CZP treatment if he/she met all inclusion and exclusion criteria at the start of CZP treatment. Written data consent must be obtained no later than the start of Visit 2 and prior to conducting any clinical assessment at Visit 2. Following written data consent (ie, enrollment into the study), all relevant data from original records will be entered onto study-specific forms.
- 2. Patient is considered reliable and capable of adhering to the observational plan (eg, able to understand and complete questionnaires, visit schedule, or medication administration according to the judgment of the treating physician.
- 3. Patient is male or female ≥18 years of age diagnosed with moderate to severe, active RA and is eligible for treatment with CZP therapy.
 Note: Patients enrolled into the study after the start of CZP treatment must have had a DAS28 score at the start of CZP treatment that is documented in their original records and indicates moderate to severe RA.
- 4. The decision to prescribe CZP has been made by the treating physician independently of his/her decision to include the patient in the study.
- 5. The patient's treatment must be within the terms of the SmPC.

Confidential Page 20 of 89

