12.1 Definition of analysis sets

The analysis set for the efficacy variables will be the Full Analysis Set. The Full Analysis Set is defined as all patients with a DAS28 ≥2.6 who took at least one dose of CZP and had at least one valid post-Baseline DAS28 value.

Note: the Full Analysis Set is defined in this way because patients who had a Baseline DAS28 value <2.6 would already be in remission. Therefore, the primary efficacy variable to reach clinical remission would not be defined.

The analysis set for the safety variables will be the Safety Set (SS), which is defined as all patients who took at least one dose of CZP.

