12.3 Planned efficacy analyses

12.3.1 Analysis of the primary efficacy variable

A patient is defined to have reached clinical remission if they show a DAS28 of <2.6. The absolute and relative number of patients in remission will be presented. Additionally, the respective 95% confidence interval (CI), constructed from an approximation to the Normal distribution, will be determined for the remission rate.

Evaluation will be done for subgroups defined by the following variables:

• Response at Visit 2 or Visit 3 (after approximately 6 and/or 12 weeks) defined by reduction in DAS28 by ≥1.2

Confidential Page 35 of 89

- Presence of relevant auto-antibodies at Baseline (cut-off depends on test used, eg, immunoglobulin M-RF enzyme-linked immunosorbent assay: ≥0.110 optimetric density; Latextest: >20IU)
- Presence of anticytoplasmatic antibodies (aCCP antibodies or anti-mutated citrullinated vimentin [MCV]); threshold for aCCP positive patient at Baseline >50Units; threshold for anti-MCV positive patient at Baseline >50Units/mL
- Pretreatments with other anti-TNF agents
- Pretreatments with other biologics
- Duration of RA disease (<2 years vs. ≥2 years)

The remission rates between subgroups and their associated 95% CIs will be compared numerically only.

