12.7 Determination of sample size

As no information on the expected remission rate for a 2-year study under real life conditions are available, an overall remission rate of 50%, which is the worst case for sample size calculation, was used for determination of sample size. Assuming this remission rate, a total of 1068 patients is sufficient to estimate with 95% confidence the overall remission rate with a precision of $\pm 3.0\%$. Furthermore, subgroups of about 500 patients are sufficient to estimate the remission rate for each subgroup (as defined in Section 12.3.1) separately with an adequate precision ($\pm 4.5\%$).

In case the overall remission rate is much lower or higher (15% / 85%) a total of 1068 patients is sufficient to estimate with 95% confidence the overall remission rate with a precision of $\pm 2.1\%$.

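### Subgroup remission rates are compared crudely on an absolute DAS28 cut-point, with no display of Baseline DAS28 or of DAS28 change, so a gap may partly reflect starting severity

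*Protocol*

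**What the plan says.** Section 3.3 (Other objectives) asks for "Assessment of clinical remission and low disease activity for all patients by visit and for different patient populations, based on DAS28" and, since Amendment 3, also on the ACR/EULAR 2011 criteria.

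Section 12.3.1 names six subgroup factors for the primary variable: early response at Visit 2 or 3, auto-antibodies, anticytoplasmatic antibodies, earlier anti-TNF treatment, earlier treatment with other biologics, and disease duration. It fixes the method of comparison: "The remission rates between subgroups and their associated 95% CIs will be compared numerically only". Section 12.2 confines every variable to descriptive statistics.

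On starting severity, section 6.1 requires a patient "diagnosed with moderate to severe, active RA and is eligible for treatment with CZP therapy" and gives no DAS28 number. Patients enrolled after starting CZP need a documented DAS28 consistent with that severity, again without a number. Section 12.1 limits the Full Analysis Set to "all patients with a DAS28 ≥2.6 who took at least one dose of CZP" with a valid later value. Its note explains that patients below 2.6 at Baseline would already be in remission.

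The DAS28 variables in section 4.1.3 are remission by visit, low disease activity (≤3.2) by visit, discontinuation because of remission, and "Proportion of patients achieving clinical response to treatment based on DAS28 reduction of ≥1.2 by visit". CDAI, pain, fatigue, HAQ-DI, EQ-5D VAS, morning stiffness and joint counts each have a change variable. DAS28 has none.

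Section 12.7 treats subgroup estimation as a design aim: "subgroups of about 500 patients are sufficient to estimate the remission rate for each subgroup", with a stated precision of ±4.5%.

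**The concern.** Remission is a fixed end value. If two subgroups follow the same relation between Baseline and follow-up DAS28, the one that starts lower will show more remission. The note in section 12.1 recognises that the starting value matters at 2.6, but above 2.6 the plan makes no further use of it in the subgroup comparison.

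Pretreated and untreated patients, or patients with short and long disease, may well start at different levels. A difference in crude rates then mixes starting severity with whatever else distinguishes the subgroups. The confidence interval does not warn of this, because it reflects sampling error only.

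The ≥1.2 response rate depends on Baseline in the opposite direction. A reader could see a subgroup that looks better on remission and worse on response when nothing differs except the starting level. The continuous summary that would help to explain this is not planned for DAS28.

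**Working it through.** **1. The plan's own figures.** Section 12.7 uses "an overall remission rate of 50%, which is the worst case for sample size calculation" and states that "a total of 1068 patients is sufficient to estimate with 95% confidence the overall remission rate with a precision of" ±3.0%.
- n = (1.96/0.03)² × 0.5 × 0.5 = 1067.1, rounded up to 1068. This reproduces.
- Half-width for one subgroup of 500 at 50%: 1.96 × √(0.25/500) = 4.4 points, against the stated ±4.5%.

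**2. The right yardstick for a gap.** The 4.4 points belong to one rate. For a difference between two independent subgroups of 500, the half-width is 1.96 × √[p₁(1−p₁)/500 + p₂(1−p₂)/500]. At 37.9% and 33.6% this is 1.96 × √(0.379×0.621/500 + 0.336×0.664/500) = 5.9 points. At the rates in step 4 it is 6.0.

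**3. A hand check (assumed inputs).** Let Visit 9 DAS28 be Normal with SD 1.3 and mean 3.0 in one subgroup. The other starts 0.5 higher, and the slope of follow-up on Baseline is 0.3, so its mean is 3.0 + 0.3×0.5 = 3.15.
- Φ((2.6−3.00)/1.3) = 37.9%
- Φ((2.6−3.15)/1.3) = 33.6%
- Gap: 4.3 points, with no other difference between the subgroups.

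**4. The same with the analysis floor (assumed inputs).** Baseline DAS28 is Normal with SD 1.2, cut off below 2.6, with means 4.75 and 5.25 before the cut. Follow-up = 3.0 + b(Baseline − 5) + error, with b = ρ×1.3/1.2 and error SD 1.3√(1−ρ²). The outcome model is the same in both subgroups. Averaging over the truncated Baseline distribution gives:

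| ρ | slope b | Remission, lower vs higher Baseline | Gap | Response ≥1.2, lower vs higher | Gap |
|---|---|---|---|---|---|
| 0.2 | 0.22 | 38.8% vs 36.1% | +2.8 | 66.8% vs 74.4% | −7.5 |
| 0.3 | 0.33 | 39.3% vs 35.1% | +4.2 | 68.3% vs 75.1% | −6.8 |
| 0.5 | 0.54 | 40.3% vs 33.3% | +7.0 | 72.2% vs 77.3% | −5.1 |

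Gaps are taken before rounding. The floor narrows the Baseline contrast slightly. With z = (mean − 2.6)/1.2, the truncated mean is mean + 1.2φ(z)/Φ(z). This gives 4.85 and 5.29, so the 0.5-point difference becomes about 0.44 in the analysed set.

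With means 1.0 apart (4.5 and 5.5), the remission gap runs from 5.5 to 13.8 points over the same correlations.

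**5. Change is not free of Baseline either.** In this model the difference in mean fall for a 0.5-point Baseline difference is 0.5×(1−b). That is 0.39 at b = 0.22 and 0.23 at b = 0.54, larger in the subgroup that starts higher. DAS28 change therefore has to be read together with Baseline.

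**The case against.** The strongest reply is that nothing here is an error. The study is noncomparative and exploratory, no test or causal reading is planned, and a crude rate correctly describes how each population fares. Starting severity may be part of what a pretreated or long-duration population is. Section 12 also leaves detail to the SAP, which is not at hand and may well tabulate Baseline DAS28 by subgroup. Adjustment would remove one confounder among many, since concomitant treatment is left to the physician.

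Much of this stands. It is why the crude rates should remain the main result and why this is an improvement rather than a correction. It does not dispose of the point, because the protocol itself fixes the method of comparison in sections 12.2 and 12.3.1, and a supportive standardised rate would not fit that wording.

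A reader might infer more than the text supports:
- **That low disease activity is also compared between subgroups.** Section 12.3.1 compares remission rates only. Section 3.3 speaks of assessment, and section 12.3.2 of descriptive statistics.
- **That severity at entry is unrestricted.** Moderate to severe active disease is required, and the efficacy set has a floor of 2.6. Only a numeric entry limit is absent.
- **That every planned result ignores Baseline.** The ≥1.2 response is a cut-point on change, and CDAI change is continuous. However, neither is a continuous DAS28 result, and the subgroup evaluation is stated only for the primary variable.
- **That the subgroups do differ at Baseline.** The protocol contains no evidence on this.

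**Conclusion.** The point holds as a recommended improvement. The protocol prescribes a crude comparison of subgroup remission rates on an absolute cut-point, uses Baseline DAS28 only as a filter, and plans no continuous change in the score behind the primary endpoint. A subgroup gap can therefore partly reflect starting severity, and the planned DAS28 results would not show how much.

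The size rests wholly on assumed inputs. With follow-up SD about 1.3 and correlation 0.2 to 0.5, a 0.5-point difference in mean Baseline DAS28 gives about 3 to 7 points of remission. That is comparable to the sampling half-width of about ±5.9 points for a difference between two subgroups of 500. It is enough to create or hide an apparent contrast, but it does not exceed sampling error throughout the range. Much larger gaps follow only if Baseline differences are bigger or persist undiminished for two years (slope 1.0), and nothing in the protocol supports either. It would also be wrong to judge a gap between two subgroups against the ±4.5% stated for one.

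**What to change.** 1. **Section 12.3.1.** Keep the crude remission rates with 95% CIs as the main descriptive result, and show mean Baseline DAS28 for each subgroup beside them.
2. **Section 12.3.1, supportive.** Apply this to the factors fixed at Baseline: auto-antibodies, anticytoplasmatic antibodies, anti-TNF pretreatment, pretreatment with other biologics, and disease duration. For each, add the remission rate with 95% CI standardised to the Full Analysis Set distribution of Baseline DAS28, for example marginal rates from a logistic model with the factor and continuous Baseline DAS28. Leave out early response, which is measured after Baseline and defined through it.
3. **Section 4.1.3.** Add change from Baseline in DAS28 by visit, summarised descriptively overall and by subgroup. State that it is to be read together with Baseline.
4. **Section 12.3.1, wording.** Amend the sentence that limits the comparison to a numerical one, so that it allows the supportive rates and says that the contrasts remain exploratory.

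The cost is a few lines of text and one extra table per factor. Baseline DAS28 is needed for membership of the Full Analysis Set, and section 9.8 already has the score computed in the database. The downside is one simple supportive model in an otherwise descriptive plan. It removes Baseline DAS28 only and leaves other confounders in place.

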3.4 Safety objectives

To assess safety data collected in a real life setting in a defined patient population (age, gender, etc.) treated with CZP. Identified and potential risks are specified in the current version of the SmPC.

4 STUDY VARIABLES

4.1 Efficacy variables

4.1.1 Primary efficacy variable

Clinical remission at Visit 9 (around Week 104) (defined as DAS28 of <2.6).

4.1.2 Secondary efficacy variables

- Change from Baseline in patient's arthritis pain as measured by Patient's Assessment of Arthritis Pain VAS at Visit 9 (around Week 104)
- Change from Baseline in patient's physical function as measured by the HAQ-DI (by Fries et al, 1980 and Lautenschläger et al,1997) at Visit 9 (around Week 104)
- Change from Baseline in disease activity measured by CDAI at Visit 9 (around Week 104)

